5.1. Pre-treatment Criteria

5.1.1. Screening Visit: Patients must meet criteria at screening as outlined in Section 3.1.

5.1.2. Hematologic Parameters for treatment:

Absolute Neutrophil Count:

- Cycle 1, Day 1: $\geq 1500/\text{mm}^3$
- Cycles 2 and Beyond, Day 1: $\geq 1000/\text{mm}^3$

For Phase 1-T patients:

- Hemoglobin:
 - Cycle 1, Day 1: $\geq 10\text{g/dL}$
 - Cycles 2 and beyond, Day 1: Per Table in Section 6.3.1
- Platelets:

- Cycle 1, Day 1: $\geq 100,000/\text{mL}$
- Cycles 2 and beyond, Day 1: Per Table in Section 6.3.1

5.1.3. All Cycles, Day 1: Patients must have all of the following:

- Adequate blood pressure control as detailed in Section 6.3.2.
- Serum creatinine $\leq 1.5 \times$ the institutional upper limit of normal
- Liver function test $\leq 2.5 \times$ upper limit of normal.
- ECOG performance status of 0 or 1.
- No evidence of life-threatening medical problems.

5.1.4. Pre-Cycle 1 Therapy: Translational Component

- All patients will be *strongly* encouraged to participate in the translational component of the trial. Travel to and from the NCI and all costs of imaging, blood draws, biopsy, or fluid sampling done at the NCI will be provided in kind. A stipend to assist with cost of the local stay during this aspect of the trial will be provided, or the patient can elect hospital admission at no cost.
- Biopsiability will be determined prior to scheduling the NCI visit using most recent tumor imaging. This will be followed by an on-study chest/abdominal/pelvic CT with oral and IV contrast obtained the day of evaluation at NCI. A copy of this scan will be provided to the home institution for use in subsequent tumor measurements.
- Patients will be seen at NCI with a copy of their signed protocol consent from their home institution.
- Drug therapy will be initiated after acquisition of initial translational components and dispensed for the 28-day cycle.
- Translational component sample acquisition will occur:
 - Prior to starting therapy
 - Prior to day 3: 2-8 hours after the 5th dose of olaparib (d1 will start with the am dose) and the 3rd dose of cediranib (the first dose of cediranib will be administered at the same time as the first dose of olaparib).

Process	Pre-treatment	Day 3
Blood for PBMCs, DNA, and CECs	X	X
Plasma and serum for cytokines	X	X
DCE-MRI imaging	X	X
Biopsy: core of tumor, involved skin, or malignant effusion sampling	X	X

5.2. Agent Administration

5.2.1. Cediranib

Cediranib at the appropriate dose level will be given orally continuously each morning on an empty stomach, either 1 hour before or 2 hours after breakfast. Subjects should not “make up” a missed dose or a dose that was vomited. Subjects should take cediranib with a glass of water. Subjects should avoid grapefruit juice while on study, due to P450 interactions. Cediranib may be taken at the same time as the morning olaparib dose.

Cediranib will be dispensed at the start of each cycle. Patients will be provided with a pill diary for each drug (Appendix B), instructed in its use, and asked to bring it with them to each appointment.

Frequent blood pressure monitoring is important in patients receiving cediranib. Clinical trials of cediranib demonstrate that increases in blood pressure may occur following dosing with cediranib for a number of weeks and that these increases may occur relatively quickly when starting the drug. Patients will be asked to record twice-daily blood pressure readings (Appendix C). If two successive systolic readings are >140 mmHg OR two successive diastolic readings are >90 mmHg OR any combination of elevated systolic and diastolic blood pressure are observed, patients will be instructed to contact their physician as soon as possible. Patients should seek medical advice if their BP exceeds 180 mmHg (systolic) or 105 mmHg (diastolic) at any time and should also be encouraged to contact their physician if they are concerned about any symptoms that may be associated with high blood pressure (e.g., headache). Section 6 includes specific guidelines on the management and, if appropriate, dose modifications for treatment-emergent hypertension.

5.2.2. Olaparib

Olaparib Capsules (Phase I and Phase II Participants)

Olaparib at the appropriate dose level will be given orally continuously twice daily on an empty stomach. The correct number of 50mg capsules comprising the appropriate dose should be taken at the same times each day with approximately 240 mL of water. Patients should take olaparib on an empty stomach either 1 hour before or 2 hours after meals. The olaparib capsules should be swallowed whole and not chewed, crushed, dissolved, or divided.

Olaparib will be dispensed at the start of each cycle. Patients will be provided with a pill diary (Appendix B), instructed in its use, and asked to bring it with them to each appointment.

If vomiting occurs shortly after the olaparib capsules are swallowed, the dose should only be replaced if all of the intact capsules can be seen and counted. Should any patient enrolled on the study miss a scheduled dose, the patient will be allowed to take the scheduled dose up to a maximum of 2 hours after that scheduled dose time. If greater than 2 hours after the scheduled dose time, the missed dose should not be taken, and the patient should take their allotted dose at the next scheduled time.

Olaparib Tablets (Phase I-T Participants)

Olaparib at the appropriate dose level will be given orally continuously twice daily on an empty stomach. The correct number of 25mg, 100mg, or 150mg tablets comprising the appropriate dose should be taken at the same times each day with approximately 240 mL of water. Patients should take olaparib on an empty stomach either 1 hour before or 2 hours after meals. The olaparib tablets should be swallowed whole and not chewed, crushed, dissolved, or divided.

Olaparib will be dispensed at the start of each cycle. Patients will be provided with a pill diary (Appendix B), instructed in its use, and asked to bring it with them to each appointment.

If vomiting occurs shortly after the olaparib tablets are swallowed, the dose should only be replaced if all of the intact tablets can be seen and counted. Should any patient enrolled on the study miss a scheduled dose, the patient will be allowed to take the scheduled dose up to a maximum of 2 hours after that scheduled dose time. If greater than 2 hours after the scheduled dose time, the missed dose should not be taken, and the patient should take their allotted dose at the next scheduled time.

5.3. Definition of Dose-Limiting Toxicity

Toxicity assessments will be done using NCI Common Terminology Criteria for Adverse Events (CTCAE v4.0). CTCAE v4.0 is identified and located on the CTEP website at (http://ctep.cancer.gov/protocolDevelopment/electronic_applications/ctc.htm). Dose-limiting toxicity (DLT) refers to toxicities experienced during the first cycle of treatment. A DLT is defined as any of the following:

- **Non-Hematologic Toxicity**
 - Grade 3 or 4 events, excluding
 - Grade 3 fatigue
 - Grade 3 hypertension controlled with anti-hypertensive therapy.
 - Grade 3 hypophosphatemia
 - Grade 3 hyponatremia
- **Hematologic Toxicity**
 - Grade 4 neutropenia of ≥ 4 days duration
 - Grade 4 neutropenia of any duration with fever or documented infection
 - All other hematologic toxicities of Grade 4
 - Inability to take 75% or more of the planned dose in Cycle 1 due to treatment-related AEs

Management and dose modifications associated with the above adverse events are outlined in Section 6 (Expected Toxicities and Dosing Delays/Dose Modifications).

Dose escalation will proceed within each cohort according to the following scheme.

Number of Participants with DLT at a Given Dose Level	Escalation Decision Rule
0 out of 3	Enter 3 participants at the next dose level.
≥ 2	Dose escalation will be stopped. This dose level will be declared the maximally administered dose (highest dose administered). Three (3) additional participants will be entered at the next lowest dose level if only 3 participants were treated previously at that dose.
1 out of 3	Enter at least 3 more participants at this dose level. 
 • If 0 of these 3 participants experience DLT, proceed to the next dose level. • If 1 or more of this group suffer DLT, then dose escalation is stopped, and this dose is declared the maximally administered dose. Three (3) additional participants will be entered at the next lowest dose level if only 3 participants were treated previously at that dose.
≤ 1 out of 6 at highest dose level below the maximally administered dose	This is generally the recommended phase II dose. At least 6 participants must be entered at the recommended phase II dose.

If one patient develops a DLT, then the cohort will be expanded to include a total of 6 patients. If greater than or equal to two patients develop DLT, then that dose level will be considered the maximum administered dose (MAD), and further dose escalation will be terminated. A total of 6 patients will be treated at the next lower dose. The maximum tolerated dose (MTD) will be the dose at which no more than 1 patient develops DLT when at least 6 patients have been treated.

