5. TREATMENT PLAN

Treatment will be administered on an outpatient basis. Expected toxicities and potential risks as well as dose modifications for cediranib and olaparib are described in Section 6 (Expected Toxicities and Dosing Delays/Dose Modifications). No investigational or commercial agents or therapies other than those described below may be administered with the intent to treat the participant's malignancy.

Phase I

Each cycle will be 28 days (4 weeks). For the Phase I component of this study, treatment cohorts will consist of 3 to 6 patients and the dose escalation schedule will be as follows. Participants enrolled to the Phase I portion of the study will continue treatment with olaparib capsule formulation.

	Dose Level	Cediranib	Olaparib (capsule)
	-1	15mg PO daily	100mg PO BID
Starting dose →	0	20mg PO daily	100mg PO BID
	1	20mg PO daily	200mg PO BID
	2	30mg PO daily	200mg PO BID
	3	30mg PO daily	400mg PO BID

Phase I-T

For the Phase I-T component of this study, treatment cohorts will consist of 3 to 6 patients. Two separate cohorts of dose escalation will be accrued, one with a dosing of cediranib at 30mg daily (Phase I-TA) and a second at cediranib dosing of 20mg daily (Phase I-TB). The two Phase I-T

dose escalation schemes will enroll in parallel. Participants enrolled to the Phase I-T portion of the study will receive treatment with the olaparib tablet formulation. The dose escalation schedule for the two cohorts will be per the following tables. If the cohort of patients enrolled in a given dose level completes the DLT assessment window without experiencing a DLT in the first three patients or with 1 or fewer DLTs in six patients, the next higher dose level may be assessed.

Phase 1-TA Dose Escalation: Cediranib 30mg

	Dose Level	Cediranib	Olaparib (tablet)
	-1-TA	30mg PO daily	100mg PO BID
Starting dose →	0-TA	30mg PO daily	150mg PO BID
	1-TA	30mg PO daily	200mg PO BID
	2-TA	30mg PO daily	250mg PO BID
	3-TA	30mg PO daily	300mg PO BID

Phase 1-TB Dose Escalation: Cediranib 20mg

	Dose Level	Cediranib	Olaparib (tablet)
	-1-TB	20mg PO daily	150mg PO BID
Starting dose →	0-TB	20mg PO daily	200mg PO BID
	1-TB	20mg PO daily	250mg PO BID
	2-TB	20mg PO daily	300mg PO BID

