Toxicity assessments will be done using NCI Common Terminology Criteria for Adverse Events (CTCAE v4.0). CTCAE v4.0 is identified and located on the CTEP website at (http://ctep.cancer.gov/protocolDevelopment/electronic_applications/ctc.htm). Dose escalation to the next dose level will occur when the preceding cohort reaches the end of Cycle 1. Patients who do not complete both treatments in cycle 1 for reasons other than cediranib or olaparib toxicity will be replaced. Toxicity data for each cohort will be reviewed prior to dose escalation. Intra-patient dose escalation will be allowed at the discretion of the investigator and overall trial PI for patients following their completion of Cycle 2 if the following criteria are met: the patient had no > grade 1 toxicities secondary to study treatment except for grade 2 or 3 HTN or nausea no greater than grade 1 after treatment with concurrent medications, the subsequent dose cohort has completed Cycle 1, and evaluation of DLTs has been completed for the subsequent dose cohort and the dose was deemed to be safe due to ≤ grade 2 toxicities. Dose escalation will occur for both cediranib and olaparib according to the dose escalation schema. Patients can be dose-escalated multiple times as long as they continue to meet criteria and do not exceed the final protocol-specified dose level (dose Level 3). All intra-patient dose escalations must be discussed and approved by the overall trial PI. If treatment-related toxicities related to one of the study drugs restricts further escalation of that drug, a modification to the dose escalation schema may be considered.

Phase I-T PK expansion

Once the MTD has been established during the Phase 1-T, two PK expansion cohorts of 6 evaluable patients each will be enrolled for pharmacokinetic studies. Participants in this expansion will receive a one week of either single-agent cediranib (Cohort 1-T PKced) or single-

agent olaparib (tablet formulation; Cohort 1-T PKolap) prior to starting cycle 1 of combination cediranib and olaparib (tablet formulation). Full details of the PK evaluation schedule are outlined in Section 8.14. Participants must be able to continue on study drug without any dose holds through Cycle 1 Day 16 of treatment to be considered fully evaluable for PK studies.

Participants participating in the PK expansion cohorts will take their study drugs on the following schedule once combination dosing has started:

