- **General Disorders**
The most common general AE reported was fatigue, which was observed in 52 patients (53%). Cases of fatigue were generally intermittent and of mild to moderate intensity (CTC grade 1 or 2). Other Aes included pyrexia (10 patients, 10%) and peripheral edema (16 patients, 16%).
- **Cardiac Disorders**

29 patients reported mild (CTC grade 1), asymptomatic tachycardia. None of these cases required treatment, and all events were considered to be unrelated to study drug.

- **Nervous System Disorders**

The most common nervous system Aes reported were headache (15%), dizziness (11%), and dysgeusia (13%). Other reported Aes included somnolence, attention or mental impairment, cognitive disorder, dizziness, depression, and memory impairment.

- **Hematologic Disorders**

Laboratory findings and/or clinical diagnoses of anemia (generally mild to moderate, CTC grade 1 or 2), neutropenia (predominantly mild to moderate, CTC grade 1 or 2), and thrombocytopenia (generally mild to moderate, CTC grade 1 or 2, sometimes severe) were observed. The incidence of anemia was 26%, neutropenia was 1%, and thrombocytopenia was 5%. A few cases of myelodysplasia have been reported on studies including olaparib. Additionally, data from study D0810C00002 have demonstrated increases in MCV in approximately 30% of patients, especially in those receiving greater than 6 cycles of treatment, mild and moderate in intensity, and asymptomatic in nature. No clinical consequences have been associated with this finding.

MDS/AML have been reported in <1% of patients exposed to olaparib. The cases were typical of secondary MDS/therapy-related AML. The duration of therapy with olaparib in patients who developed secondary MDS/AML varied from <6 months to >2 years. All patients had potential contributing factors for the development of MDS/AML, having received extensive previous chemotherapy with platinum agents. Many had also received other DNA damaging agents.

New primary malignancies have been reported in a small number of patients. There were other contributing factors/potential alternative explanations for the development of the new primary malignancy in all cases.

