Pneumonitis events have been reported in <1% of patients receiving olaparib. The reports of pneumonitis had no consistent clinical pattern and were confounded by a number of pre-disposing factors (cancer and/or metastases in lungs, underlying pulmonary disease, smoking history, and/or previous chemotherapy and radiotherapy).

6.2. **Dose Modifications/Delays**

In the phase 1 and phase 1-T components of this study, doses of cediranib and olaparib will be administered at the same dose level throughout a cycle if no DLTs occur. In cycle 1, patients experiencing non-hematologic Grade 2 Aes (or Grade 3 fatigue or hypertension) may have treatment held for up to 7 days for toxicity management. Treatment may then be resumed at the same dose level. Inability to take at least 75% of the planned dose of cediranib and olaparib in Cycle 1 due to drug-related toxicity is considered a DLT. If any individual patient develops a DLT, treatment for this patient will be stopped. If the toxicity is not resolved within 14 days, the patient will be removed from the study. Patients who experienced a DLT whose toxicity has

resolved to baseline or Grade 1 and whose therapy has been discontinued for less than 14 days may resume therapy at the previous (next lower) dose level if necessary. For patients who experience a DLT in the first cycle of the first cohort (cediranib 20mg daily and olaparib 100mg BID) whose toxicity has resolved to baseline or Grade 1 and whose therapy has been discontinued for less than 14 days, the dose may be reduced to cediranib 15mg daily and olaparib 100mg BID. During the DLT assessment period, both drugs must be held if there is an indication for either drug to be held.

For patients experiencing non-hematologic Grade 2 Aes (or Grade 3 fatigue or hypertension) in cycles 2 or greater, treatment may be held for up to 14 days for toxicity management if necessary. The treating physician may decide to hold treatment to ensure patient safety when grading and/or attribution is unclear. Patients whose treatment has been held for ≤ 7 days may then resume treatment at the same dose level. If treatment is held for > 7 days, please see Section 6.3.1 regarding dose modifications. For patients in the phase 1 and 1-T portions of the study in cycles 2 and beyond, dose modifications/delays should be managed as per Section 6.3.1. Tables for cediranib and olaparib dosing levels are provided in Sections 6.2.1 and 6.2.2.

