9. STUDY CALENDAR

Baseline evaluations are to be conducted within 2 weeks prior to start of protocol therapy. Scans and assessment of cardiac function must be done ≤ 4 weeks prior to the start of therapy. In the event that the participant's condition is deteriorating, laboratory evaluations should be repeated within 48 hours prior to initiation of the next cycle of therapy.

All assessments must be performed prior to administration of any study medication. All study assessments and medications should be administered within ± 3 days of the protocol-specified date, unless otherwise noted. After completion of the first two cycles, cycle visits and associated studies can be performed within ± 7 days of the protocol-specified date, unless otherwise noted. The study calendar for the Phase I and II portions of the study are as per the following pages:

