9.1. Study Calendar: Phase I and Phase I-T

	Pre-Study	Prior to Each Cycle ^{a,o}	Cycles 1 & 2 Day 8, 15, 22 (+/- 3 days)	Every 2 Cycles	Off Treatment
Informed Consent ^a	X ^a				
Medical History	X				
Concomitant Medications ^b	X ^b	X ^b	X ^b		X ^b
Adverse Event Assessment		X	X		X
Vital Signs ^c	X ^c	X ^c	X ^c		X ^c
BP Measurement at Home (See Appendix C)		Twice a day while on study			
Physical Exam	X	X	X		X
Height	X				X
Weight	X	X			
ECOG Performance Status ^d	X ^d	X ^d			X ^d
CBC with Differential	X	X	X		X
Serum Chemistry ^e	X ^e	X ^e	X ^e		X ^e
INR and PTT	X				
Troponin T or I TSH and Free T4 ^f	X ^f	X ^f			X ^f
Urinalysis ^g	X ^g	X ^g	X ^g		X ^g
Electrocardiogram	X	X ^h			
MUGA or Echocardiogram ⁱ	X			X	
Pregnancy Test ^j	X ^j				
CA-125 Measurements ^k	X ^k	X ^k			
Tumor Measurements ^{l,m}	X ^l			X ^{l,m}	
Review of BP diary by study team		X	X		
Pharmacokinetics ^p		X	X		

- a: Informed consent will be obtained prior to any study-related screening tests. For Cycle 1 Day 1, physical examination and laboratory evaluations do not have to be repeated if they have been performed at screening within 7 days of Cycle 1 Day 1.
- b: Because of a potential for interaction of cediranib and olaparib with other drugs through the cytochrome P450 system, the Principal Investigator should be alerted if the patient is taking any other medications known to affect P450 isoenzymes.
- c: Temperature, pulse, blood pressure
- d: See Appendix A for ECOG performance status
- e: Sodium, potassium, chloride, bicarbonate, BUN, creatinine, glucose, albumin, calcium, phosphorus, AST (SGOT), ALT (SGPT), alkaline phosphatase, total bilirubin, LDH.
- f: Pre-study and prior to the first 2 cycles, then as clinically indicated, and at off-study visit.
- g: A urine protein:creatinine ratio may be used instead. See Section 6.3.3 Management of Proteinuria if dipstick at least 1+ on study.
- h: ECG done prior to Cycle 1 and 2, and then prior to every cycle if clinically indicated.

- i: MUGA or echocardiogram should be done at baseline and every other cycle for those patients at increased risk for compromised LVEF. Increased risk patients have had one or more of the following: (1) prior treatment with anthracyclines, (2) prior treatment with trastuzumab, (3) NY Heart Association classification of II, (4) prior central thoracic RT, (5) history of myocardial infarction within the 12 months prior.
- j: beta-HCG for women of childbearing potential.

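### In Phase I-T cycle 1, the required blood counts cannot show whether an isolated, uncomplicated Grade 4 neutrophil count is a DLT

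*Combined protocol and SAP*

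**What the plan says.** Section 5.3 of the combined protocol and SAP gives three ways in which neutropenia in cycle 1 can become a DLT:

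- by duration alone: "Grade 4 neutropenia of ≥ 4 days duration";
- by complication: "Grade 4 neutropenia of any duration with fever or documented infection";
- by lost dosing: the patient cannot take 75% of the planned cycle-1 dose because of treatment-related events (repeated in 6.2).

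Calendar 9.1, which governs Phase I and Phase I-T, marks a CBC with differential before each cycle and in the column headed "Cycles 1 & 2 Day 8, 15, 22 (+/- 3 days". The CBC row has no footnote about extra counts. The general text of Section 9 has one repeat-laboratory rule, for a patient whose condition is deteriorating: "laboratory evaluations should be repeated within 48 hours prior to initiation of the next cycle of therapy".

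Section 5 says of escalation: "Toxicity data for each cohort will be reviewed prior to dose escalation". For Phase I-T, a level is passed with no DLT in the first three patients or "with 1 or fewer DLTs in six patients, the next higher dose level may be assessed". Section 6.2 adds: "If any individual patient develops a DLT, treatment for this patient will be stopped".

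**The concern.** The duration criterion turns on a 4-day threshold, but the scheduled counts are about a week apart. A single Grade 4 value between two values that are not Grade 4 could come from an episode of less than a day or of well over a week. The protocol has no rule for classing it.

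MTD and DLT are the Phase I-T primary endpoint (14.1.4), and escalation rests on cohorts of 3 to 6. One patient classed differently can change the action taken. The class also decides that patient's own care, because a DLT stops treatment. The cohort review before escalation cannot recover a count that was never taken.

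**Working it through.** **The plan's own figure.** The escalation table in 14.1.3 depends on DLT counts. With true DLT rate p, P(escalate) = (1−p)³ + 3p(1−p)² × (1−p)³. At p = 0.2 this is 0.512 + 0.384 × 0.512 = 0.709 (stated 0.71). All ten stated values reproduce. The table is correct, but it takes each patient's DLT status as known.

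**Bracket around an isolated Grade 4 count.** Inputs: CBCs on Days 1, 8, 15 and 22 and on Cycle 2 Day 1 (Day 29). The ±3 days comes from 9.1, and for Day 29 from the general rule in Section 9. The bracket is the later neighbouring count minus the earlier one.

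| Grade 4 count at | Nominal | Shortest | Longest |
|---|---|---|---|
| Day 8 | 15 − 1 = 14 | 12 − 1 = 11 | 18 − 1 = 17 |
| Day 15 | 22 − 8 = 14 | 19 − 11 = 8 | 25 − 5 = 20 |
| Day 22 | 29 − 15 = 14 | 26 − 18 = 8 | 32 − 12 = 20 |

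The Day 8 row assumes that the baseline count is taken on Day 1. Footnote a of 9.1 lets a screening count up to 7 days earlier stand in, which would only widen the bracket. In every permitted schedule the possible duration runs from under 1 day to just under the bracket, so it always includes both sides of 4 days.

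**What weekly counts show (illustration).** Assume nominal dates, an onset equally likely at any point in the week, and true duration d. For d ≤ 7, P(exactly one Grade 4 count) = d/7 and P(two) = 0. For d = 4, 5, 6 and 7 this gives 57%, 71%, 86% and 100%. A 3-day episode, not a DLT, is caught once in 3/7 = 43% of cases and then looks the same as a 4-day one. Two Grade 4 counts about a week apart do support at least 4 days. With the windows, however, consecutive counts can be 1 day apart (Day 11 and Day 12), so two such counts are not always proof.

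**Effect of one reclassified patient.** 0/3 (escalate) becomes 1/3, after which escalation needs no DLT in three more patients. That probability is (1−p)³ = 0.73, 0.51 or 0.34 at p = 0.10, 0.20 or 0.30. Alternatively, 1/6 (escalate) becomes 2/6 (stop).

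**How often.** The documents give no Grade 4 neutropenia rate for the combination. Section 6.1.2 reports 1% neutropenia in the first olaparib study, predominantly Grade 1 or 2. Assume that a fraction q of patients has such a count, so that P(at least one in n) = 1 − (1−q)ⁿ. Section 1.1 allows up to 30 Phase I-T patients within 28 + 90 + 30 = 148 and gives no separate line for the 12 PK-expansion patients. Those 12 enroll after the MTD is set, which leaves 30 − 12 = 18.

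| q (assumed) | n = 6 | n = 18 | n = 30, if PK patients are extra |
|---|---|---|---|
| 0.2% | 1.2% | 3.5% | 5.8% |
| 1% | 5.9% | 16.5% | 26% |
| 3% | 16.7% | 42% | 60% |

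**The case against.** Several points stand against reading this broadly.

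- **Other DLT routes.** Fever or documented infection makes Grade 4 neutropenia a DLT at any duration. A hold that leaves less than 75% of the dose also does so, and in the DLT window both drugs are held together (6.2). These cases are classed, so the gap is confined to the remainder. A hold of exactly 7 of 28 days leaves 21/28 = 75%, which is not a DLT, so the dose rule does not cover a hold lasting until the next nominal count.
- **Follow-up duties.** Section 11.1 requires events detected by laboratory test to be followed. On Phase 1 trials 11.5.1 requires 24-hour notification of Grade 4 events and a full report within 5 further days. The calendar bars no unscheduled count, and many clinicians would recheck. This makes a week without a count less likely. But none of these provisions sets a count interval, and 11.2.1 limits which laboratory values are adverse events at all. The hematologic hold in 6.3.1 implies a recovery count, again without an interval.
- **The episode model.** Olaparib is given continuously, and the documents say nothing about how long such episodes last. The 57% to 100% figures are therefore illustrative. The bracket does not depend on them.
- **Timing.** Tablet escalation may be over. The 30 mg / 200 mg dose named for the PK group in 8.14 matches both the capsule RP2D and tablet level 1-TA, so the documents do not settle it.

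A reader might infer that no Grade 4 neutropenia can be classed, that an escalation decision was wrong, or that the percentages above are chances of a wrong MTD. The documents support none of these. The other DLT routes exist, no patient data are shown, and the percentages are chances that at least one such count occurs.

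**Conclusion.** The gap is real but narrow. In Phase I-T cycle 1, an isolated Grade 4 neutrophil count without fever or documented infection, in a patient still taking at least 75% of the planned dose, cannot be classed as DLT or non-DLT from the data that the protocol requires. Following the plan exactly leaves an input to the primary endpoint undetermined in that case. The 8-to-20-day bracket rests only on the calendar and its windows, and on no unscheduled count being drawn. The frequency figures rest on assumed rates and on the 30 patients including the PK cohorts; the event is probably rare. The capsule Phase I used the same rule and calendar, but its RP2D is already fixed, so the point concerns Phase I-T.

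One separate error sits in the 6.3.1 hematologic table. Its hemoglobin limit is 8 mg/dL, which is 0.008 g/dL, and read literally it could never trigger a hold. Eligibility (3.1.7) uses g/dL. A reader will probably recognize the slip, but it is an operative threshold and should be corrected.

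**What to change.** Add to 5.3, and as a footnote to the CBC row of 9.1:

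> If a cycle-1 count shows Grade 4 neutropenia, repeat the CBC at least every 2 days until below Grade 4. Duration runs from the first Grade 4 count to the first count below Grade 4. If a missing repeat means a duration under 4 days cannot be shown, count it as a DLT.

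The cost is a few extra CBCs in a rare patient and a slightly conservative DLT count. The 2-day interval is a convention, and the rule does not recover time before the first Grade 4 count. If repeats are exactly 2 days apart and the remaining duration at detection is r, the measured duration is 2 × ceil(r/2), which reaches 4 when r > 2. Under the uniform-onset model, a detected episode with d ≤ 7 is then counted with probability (d−2)/d: 33% at 3 days, 50% at 4 days and 71% at 7 days. The rule is imperfect near the threshold, but it classes every detected episode in one stated way.

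If tablet escalation is complete, instead report beside the DLT table any cycle-1 Grade 4 neutrophil count that had no repeat within 4 days.

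Separately, change the hemoglobin limit from 8 mg/dL to 8 g/dL wherever it appears in the 6.3.1 hematologic table.
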